SOP	Standard Operation Procedure
SS	Safety Set

Abbreviation	Expanded Term
SUSAR	Suspected Unexpected Serious Adverse Reaction
TEAE	Treatment Emergent Adverse Event
VZV	Varicella Zoster Virus
WHODD	WHO Drug Dictionary
ZBPI	Zoster Brief Pain Inventory

Definitions of Terms

Month	30 days.
Women of Childbearing Age	Women from menarche until menopause are considered capable of childbearing unless it has been clearly confirmed that they have undergone a hysterectomy, bilateral salpingectomy, and bilateral oophorectomy.
Severe Medical History	Diseases requiring emergency treatment, hospitalization, and/or surgical procedures.
Antibody Positivity Rate and Antibody Seroconversion Rate	1) Abnormal antibody concentration (measured by ELISA): Specific anti-gE antibody concentration >0.1 IU/mL (or 100 mIU/mL) is defined as positive. 2) Pre-immunization antibody positivity rate: The proportion of subjects with anti-gE antibody positivity in pre-immunization serum samples. 3) Post-immunization antibody concentration ≥ 4 times the pre-immunization level is defined as seroconversion. 4) Seroconversion rate: The proportion of subjects achieving seroconversion in post-immunization serum samples.
Antibody Fold Increase	The fold increase in specific anti-gE antibody concentration (measured by ELISA) compared to the pre-immunization level.
HZ Suspected Cases	Suspected herpes zoster (HZ) cases meet at least one of the following criteria: a) Unilateral pain or rash. b) Dermatomal, unilateral distribution of grouped vesicles on an erythematous base. c) Neuralgia.

Protocol Synopsis

Study title	A randomized, blinded clinical trial to evaluate the immunogenicity and safety of the recombinant zoster vaccine (CHO cells) LZ901 compared with a similar active vaccine in subjects aged 50 years and older
Sponsor	Beijing Luzhu Biotechnology Co., Ltd. Luzhu Biopharmaceuticals (Zhuhai) Co., Ltd.
Protocol No.	LZ901-330, V1.1
Study phase	III+
Study vaccine	Recombinant zoster vaccine (CHO cells) (LZ901) Recombinant Zoster Vaccine (RZV, Shingrix™)
Indications	To prevent herpes zoster (HZ) and its complications caused by Varicella-Zoster Virus (VZV) infection.

Study Objectives

Primary objective	To evaluate the immunogenicity of cellular immune response induced by recombinant zoster vaccine (CHO cell) in subjects aged 50 years and older, in comparison to the active control vaccine.
Secondary objective	To evaluate the immunogenicity and safety of humoral immune responses induced by recombinant zoster vaccine (CHO cells) in subjects aged 50 years and older.

Study Endpoints

Primary endpoints	The proportion of specific CD4+/CD8+ T cells activating at least two cytokines (TNF- α , IFN- γ , IL-2, CD40L) 30 days after full immunization.
Secondary endpoints	
Immunogenicity endpoints
 
 1. Geometric Mean Concentration (GMC) and seroconversion rate of anti-gE antibodies 30 days after full immunization; 2. Geometric Mean Fold Increase (GMFI) in anti-gE antibodies 30 days after the whole immunization course compared to pre-immunization (Day 0). 
Safety endpoints
 
 1. Incidence of solicited adverse events (AE) within 0-7 days after each dose, including local (injection site) and systemic (non-injection site) reactions; 2. Incidence of unsolicited AEs within 0-30 days after each dose; 3. Incidence of AEs within 30 minutes after each dose; 4. Incidence of adverse events of special interest (AESIs) from the first dose through 30 days after full immunization; 5. Incidence of serious adverse events (SAEs) from the first dose through 6 months after full immunization.

Study Design

Overall design	
Study design: Randomized, partially blinded
 
Immunization schedule: Experimental vaccine at 0 and 30 days; active control vaccine at 0 and 60 days

----------------	---

	
Study groups: Experimental group and control group
 
Blinding: LZ901-330 is a partially blinded study, with a double-blind design prior to the second dose, and an open-label design at the time of the second dose.
 
Number of subjects and groups
 
Approximately 300 subjects aged 50 and older will be enrolled and randomly assigned in a 1:1 ratio to the experimental group and the control group. The experimental group will receive two doses of the recombinant zoster vaccine (CHO cell), developed and manufactured by Beijing Luzhu Biotechnology Co., Ltd. / Luzhu Biopharmaceuticals (Zhuhai) Co., Ltd., with an immunization schedule of 0 and 30 days. The control group will receive two doses of the Recombinant Zoster Vaccine (RZV, ShingrixTM), products of GlaxoSmithKline Biologicals SA, with an immunization schedule of 0 and 60 days.
																							
	
Table 1 Treatment Groups
 
  
 Age	Experimental group	Control group	Total target enrollment	
   
 50 and older	150	150	300	
  
 
Vaccine administration
 
Subjects in the experimental group will be administered two doses of the experimental vaccine on days 0 and 30, while subjects in the control group will be administered two doses of the control vaccine on days 0 and 60.
 
Study follow-up visit
 
The specific visit schedule and visit content are detailed in the "Study Schedule."
 
Immunogenicity observation: Blood samples will be collected from all subjects once before vaccination and once 30 days after full immunization, for a total of two blood samples. The ELISA method will be used to measure varicella-zoster virus (VZV) gE-specific antibodies, and flow cytometry will be used to assess VZV gE-specific CD4+/CD8+ T cell activation. The proportion of subjects activating at least two cytokines (TNF-α, IFN-γ, IL-2, CD40L) will be calculated to evaluate the vaccine humoral and cellular immune response. Detailed blood sample collection time points, volumes, and purposes are shown in the table below:
 
Table 2 Detailed blood sample collection time, volumes, and purposes
 
  
 Visit Time	Test items and blood collection volume (ml)	
 
 Serum Antibody	Cellular Immune	Total	
   
 D0	4.0-5.0	15.0-20.0	19.0-25.0	
 
 30 days after full immunization	4.0-5.0	15.0-20.0	19.0-25.0	
  
 
Note: Serum antibody testing is performed using procoagulant tubes for blood collection; cellular immunity indicators are tested using anticoagulant tubes for blood collection.
 
Safety observation:
 
Collect all AEs (adverse events) within 30 days after vaccination (including solicited AEs within 30 minutes, 0-7 days, and all unsolicited AEs within 0-30 days). Follow up on all SAEs (serious adverse events) and pregnancy-related
	Age	Experimental group	Control group	Total target enrollment	50 and older	150	150	300	Visit Time	Test items and blood collection volume (ml)			Serum Antibody	Cellular Immune	Total	D0	4.0-5.0	15.0-20.0	19.0-25.0	30 days after full immunization	4.0-5.0	15.0-20.0	19.0-25.0
Age	Experimental group	Control group	Total target enrollment																					
50 and older	150	150	300																					
Visit Time	Test items and blood collection volume (ml)																							
	Serum Antibody	Cellular Immune	Total																					
D0	4.0-5.0	15.0-20.0	19.0-25.0																					
30 days after full immunization	4.0-5.0	15.0-20.0	19.0-25.0																					

	
events from the first dose of vaccination to 6 months after full immunization.
 
Solicited AEs include:
 
 
 Injection site (local) AEs	Pain, pruritus, induration, swelling, rash, redness	
 
 Non-injection site (systemic) AEs	Fatigue, tiredness, fever, headache, insomnia, myalgia, skin and mucosal abnormalities, pain at non-injection sites, diarrhea, constipation, vomiting, nausea, acute allergic reactions, arthritis, arthralgia	
 
 
Unsolicited AEs include: Any adverse event that is not a solicited AE or any solicited AE occurring outside the solicitation period (e.g., If the solicited AEs mentioned above occur more than 7 days after vaccination, they should be recorded as unsolicited AEs).
 
Collection of AESIs (Adverse Events of Special Interest):
 
Suspected cases of herpes zoster within 30 days following the first dose of vaccination to full immunization.
	Injection site (local) AEs	Pain, pruritus, induration, swelling, rash, redness	Non-injection site (systemic) AEs	Fatigue, tiredness, fever, headache, insomnia, myalgia, skin and mucosal abnormalities, pain at non-injection sites, diarrhea, constipation, vomiting, nausea, acute allergic reactions, arthritis, arthralgia
Injection site (local) AEs	Pain, pruritus, induration, swelling, rash, redness				
Non-injection site (systemic) AEs	Fatigue, tiredness, fever, headache, insomnia, myalgia, skin and mucosal abnormalities, pain at non-injection sites, diarrhea, constipation, vomiting, nausea, acute allergic reactions, arthritis, arthralgia				
study vaccine	
Experimental Vaccine:
 
Vaccine Name: Recombinant zoster vaccine (CHO Cells)
 
Specification: 100μg/0.5ml/ vial
 
Lot Number: 20230201
 
Manufacturer: Luzhu Biopharmaceuticals (Zhuhai) Co., Ltd.
 
Control Vaccine:
 
Vaccine Name: Recombinant Zoster Vaccine (RZV, ShingrixTM)
 
Specification: 50 μg/0.5 ml/vial
 
Lot Numbers: 3472D, X4937
 
Manufacturer: GlaxoSmithKline Biologicals SA
				
Study Population					
Age	Aged 50 and older				
Sex	Male and female (relatively balanced)				
Inclusion criteria	
 1. Age 50 years or older on the day of enrollment, regardless of gender, and able to provide legal identification. 2. Able to understand the trial procedures, voluntarily agree to participate in the study, and sign the "Informed Consent Form." 3. Female subjects are not pregnant or lactating. Female subjects with childbearing potential should take reliable contraceptive measures, and have no pregnancy and fertility plan within 8 months; 4. Axillary temperature \leq 37.0°C/99.0°F on the day of enrollment. 5. Able to attend all scheduled follow-up visits and able to comply with protocol requirements. 				

Exclusion Criteria	
 1. History of herpes zoster within the past 5 years. 2. Previous vaccination with varicella vaccine or zoster vaccine (including use of registered products or participation in clinical trials for varicella or zoster vaccines). 3. Allergy to any component of the study vaccine: Previous allergy to any recombinant vaccine derived from CHO cells (such as recombinant hepatitis B vaccine [CHO cells]), polysorbates, or a history of severe allergic reactions* to any vaccination. 
 a) *Severe allergic reactions: Anaphylactic shock, allergic laryngeal edema, allergic purpura, thrombocytopenic purpura, localized allergic necrotic reaction (Arthus reaction), severe urticaria, etc. 4. Diagnosis of immune deficiency diseases (such as congenital or acquired immunodeficiency, HIV infection, etc.), or receiving immunosuppressive/cytotoxic treatment (e.g., chemotherapy, organ transplantation, or planned treatment during the clinical trial within 6 months before vaccination). 5. Subjects who received immunosuppressive therapy within 3 months before vaccination, or planning to receive such treatment within 1 month after full immunization (e.g., long-term use of systemic glucocorticoids for \geq 14 days, dose \geq 2 mg/kg/day or \geq 20 mg/day prednisone or equivalence); 6. Receiving an inactivated vaccine, recombinant vaccine, or mRNA vaccine within 14 days or any live vaccine within 28 days prior to vaccination; 7. Subjects with acute illness or in the acute phase of a chronic disease within 3 days prior to vaccination. 8. Asplenia or splenectomy. 9. Subjects who receive blood products or immunoglobulin therapy within 3 months before vaccination, or planning to use such products within 2 months after vaccination. 10. Participating in other clinical studies of investigational or un-registered products (drugs, vaccines or devices, etc.), or planning to participate in other clinical studies before the end of this clinical study. 11. Any significant underlying medical condition (e.g., life-threatening diseases that may limit survival to less than 4 years) or other conditions that the investigator believes may interfere with the completion of the study.
Postponement Criteria for the Second Vaccination	
The study intervention (second dose of vaccine) should be suspended (or delayed) until the situation resolves in the following cases:
 
 1. Axillary temperature $> 37.0^{\circ}\text{C}/99.0^{\circ}\text{F}$; 2. Acute illness within 3 days prior to vaccination (e.g., acute upper respiratory infection with symptoms such as fever, cough, sore throat, difficulty breathing) or during an acute stage of a chronic disease, or use of antipyretics, analgesics, or antihistamines; 3. Insufficient interval between vaccinations (receiving an inactivated vaccine, recombinant vaccine, or mRNA vaccine within 14 days prior to vaccination, or any live attenuated vaccine within 28 days prior to vaccination); 4. Any Grade 3 or higher adverse event on the day of vaccination;

	
5. Other circumstances where the investigator considers vaccination should be delayed.

Exclusion Criteria for the Second Dose	
The investigator will terminate the administration of the second dose of the study vaccine if any of the following occur:
 
 1. Any serious adverse event (SAE) related to the vaccination; 2. Severe allergic reaction following vaccination; 3. Suspected varicella-zoster virus (VZV) infection after the first dose of immunization; 4. Discovery of any new condition that meets the "exclusion criteria for the first dose"; 5. Any other reason, as determined by the investigator, that requires discontinuation of the study vaccine administration.
Criteria for Subject Withdrawal from Study	
A subject will be withdrawn from the study if any of the following conditions occur:
 
 1. Development of intolerable severe adverse events or any condition that makes the subject unsuitable to continue participation in the study. 2. Occurrence of a severe allergic reaction related to the experimental vaccine, and the investigator assesses that the subject is no longer suitable to continue in the study. 3. The subject voluntarily withdraws from the study. 4. Poor compliance, failure to adhere to the study protocol, or loss to follow-up. 5. If an enrolled subject develops a condition during the study that makes continued participation unsuitable, and the investigator assesses that the risks of participation outweigh the potential benefits, the investigator may decide to withdraw the subject from the study.
Criteria for suspension and termination of the study	
Criteria for study suspension:
 
 1. New data regarding the study vaccine obtained from this study or any other study, or management reasons suggesting that the risks outweigh the benefits, prompting the sponsor, investigator, and/or ethics committee to recommend a suspension; 2. The occurrence of a serious adverse event that is potentially life-threatening or leads to the subject death, which may be related to the vaccination; 3. If $\geq 15\%$ of subjects experience Grade 3 or higher adverse events during the study, these events do not resolve to below Grade 3 within 48 hours. 
If the study is suspended, the ethics committee (IRB) and provincial or national drug regulatory authorities or relevant departments must be notified. An expert meeting will be conducted to assess safety, and a blinded analysis may be conducted if necessary to determine whether the study should continue. The study may resume once safety, protocol compliance, and data quality issues are resolved and the requirements of the sponsor, ethics committee, and/or national regulatory authorities are met.
 
Criteria for study termination:
 
 (1) Reaching the study endpoints; (2) Any subject experiencing a life-threatening or fatal serious adverse event

	
related to the study vaccine during the study;
 
(3) The study meets the criteria for suspension ($\geq 15\%$ of subjects experience \geq Grade 3 adverse events, and these do not resolve to below Grade 3 within 48 hours), and it is determined that these events are related to the study vaccine.
 
If the study is terminated early, the sponsor will immediately notify the investigator, clinical trial institution, ethics committee, and regulatory authorities of the reason for termination in accordance with the relevant regulatory requirements. The investigator should report to the clinical trial institution and IRB, providing a detailed written explanation.
 
Regardless of the reason for suspension or termination, the investigator must immediately inform the subjects and ensure appropriate follow-up is conducted.

Study period	Duration of participation for each subject: From the first visit to the final visit, each subject is expected to participate in the study for approximately 7 to 8 months.

Schedule of Activities

Visit	V1	V2	V3	V4	V5	V6	V7	V8
	D0	D7	D30	D37	D60	D67	D90	6 months after full immunization
Time window (day)	/	+3	-2/+7	+3	-2+7	+3	-2+7	-7+15
Signed informed consent	■							
Demographic and other basic data	■							
Medical history	■							
Physical examination ¹	■		•		★			
Inclusion criteria/Exclusion criteria	■		•		★			
Pregnancy test ²	■		•		★			
Axillary temperature	■		•		★			
Randomization	■							
Blood Collection ³	■				•		★	
Vaccination	■		•		★			
30 minutes observation	■		•		★			
Dispense and train Diary Card	■		•		★			
Review and collect Diary Card		■		•		★		
Dispense Contact Card		■		•		★		

Review and collect Contact Card			■		●		★	
Collection of Concomitant Medication	■	■	■	●	■	★	★	
Collection of Pregnancy Events	■	■	■	●	■	★	★	■
Serious Adverse Events	■	■	■	●	■	★	★	■

Note: ■: All subjects; ●: Experimental group subjects; ★: Control group subjects.

1. The physical examination includes height, weight, skin examination, blood pressure, etc. Height and weight may not be measured before the second dose.
2. Before each dose, female subjects of childbearing potential must undergo a urine pregnancy test, and the test must be negative in order to continue the study.
3. All subjects will have blood drawn before vaccination and 30 days after full immunization.

1. Introduction

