1.2.2 Risks

LZ901 Phase I clinical trial (40 subjects with study vaccine) risk summary: After receiving the experimental vaccine (both high and low doses), the occurrence of local and systemic adverse events was as follows: pain (13 cases), fatigue (4 cases), headache (4 cases), abdominal pain (2 cases), swelling (2 cases), pruritus (2 cases at the injection site), erythema (1 case), chills (1 case), myalgia (1 case), pharyngeal discomfort (1 case), maculopapular rash (1 case), pruritus (1 case at another site), and pruritic rash (1 case). These were mostly grade 1 adverse events (AEs), which resolved on their own without the need for treatment, and no grade 3 or higher AEs were observed.

Phase II clinical trial (300 subjects with study vaccine) risk summary: After receiving the experimental vaccine (both high and low doses), the occurrence of local and systemic adverse events was as follows: pain (41 cases), induration (5 cases), swelling (3 cases), erythema (9 cases), pruritus (12 cases), fatigue (18 cases), and headache (6 cases).

cases). In the high-dose group (100 µg/dose), the most common adverse event was pain at the injection site (17.45%). The severity of adverse events was as follows: grade 1 (26.85%), grade 2 (6.04%), and grade 3 (2.01%). These adverse events did not require treatment and resolved on their own. Overall, the safety of the vaccine was favorable.

Known Risks: Based on the results of Phase I and Phase II clinical trial and previous vaccine experience, intramuscular injection is an invasive procedure. Subjects may experience local adverse reactions at the injection site, such as pain, swelling, induration, erythema, and pruritus, as well as systemic reactions like fatigue, headache, fever, gastrointestinal discomfort (nausea, vomiting, diarrhea, abdominal pain), and, in rare cases, allergic reactions. Most of these adverse events are mild, do not require treatment, and resolve on their own.

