2.2.2 Secondary endpoints

Immunogenicity endpoints

- 1) Geometric Mean Concentration (GMC) and seroconversion rate of anti-gE antibodies 30 days after full immunization;
- 2) Geometric Mean Fold Increase (GMFI) in anti-gE antibodies 30 days after full immunization compared to baseline (Day 0).

Safety endpoints

1. Incidence of solicited adverse events (AE) within 0-7 days after each dose, including local (injection site) and systemic (non-injection site) reactions;
2. Incidence of unsolicited AEs within 0-30 days after each dose;
3. Incidence of AEs within 30 minutes after each dose;
4. Incidence of adverse events of special interest (AESIs) from the first dose through 30 days after full immunization;
5. Incidence of serious adverse events (SAEs) from the first dose through 6 months after full immunization.

3. Study design

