3.1.3.2 Safety observation

Collect all AEs (adverse events) within 30 days after vaccination (including solicited AEs within 30 minutes, 0-7 days, and all unsolicited AEs within 0-30 days). Follow up on all SAEs (serious adverse events) and pregnancy-related events from the first dose of vaccination to 6 months after full immunization.

Solicited AEs include:

Injection site (local) AEs	Pain, pruritus, induration, swelling, rash, redness
Non-injection site (systemic) AEs	Fatigue, tiredness, fever, headache, insomnia, myalgia, skin and mucosal abnormalities, pain at non-injection sites, diarrhea, constipation, vomiting, nausea, acute allergic reactions, arthritis, arthralgia

Unsolicited AEs include: Any adverse event that is not a solicited AE or any solicited AE occurring outside the solicitation period (e.g., If the solicited AEs mentioned above occur more than 7 days after vaccination, they should be recorded as unsolicited AEs). Collection of AESIs (Adverse Events of Special Interest): Suspected cases of herpes zoster within 30 days following the first dose of vaccination to full immunization.

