5.3 Dosage and Administration

The study vaccine is administered at a dose of 0.5 mL per person, injected intramuscularly into the deltoid muscle. As with all vaccines, the vaccination site should be equipped with appropriate emergency medical measures and have medications such as epinephrine available for use in case of a severe allergic reaction. After vaccination, the subject should be observed on-site for 30 minutes.

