6.1.2 Exclusion Criteria for the Second Dose

The investigator will terminate the administration of the second dose of the study vaccine if any of the following occur:

- 1) Any serious adverse event (SAE) related to the vaccination;
- 2) Severe allergic reaction following vaccination;
- 3) Suspected varicella-zoster virus (VZV) infection after the first dose of vaccination;
- 4) Discovery of any new condition that meets the "exclusion criteria for the first dose";
- 5) Any other reason, as determined by the investigator, that requires discontinuation of the study vaccine administration.

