7.4.7 Adverse Events of Special Interest (AESIs)

AESIs, specifically suspected cases of herpes zoster, will be collected from the first dose through 30 days after completing the full immunization.

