8.4.4 Safety

This study will primarily focus on the statistical analysis of treatment-emergent adverse events (TEAEs) occurring after vaccination. Adverse events occurring before vaccination will be listed separately. Unless otherwise specified, the term "adverse events" in the following sections refers to TEAEs.

Solicited adverse events occurring 0-7 days post-vaccination, as well as solicited adverse events related to vaccination, will be categorized and analyzed by group, type of reaction (systemic and local), and the severity of each solicited adverse event as listed in Section 3.1.3.2. For these events, the number of adverse events, the number of subjects experiencing them, and the incidence rate will be calculated.

The following adverse events will be categorized and analyzed by group, System Organ Class (SOC), and Preferred Term (PT), calculating the number of events, the number of affected subjects, and the incidence rate:

- Unsolicited adverse events occurring 0-30 days after each dose;
- Adverse events occurring within 30 minutes after each dose;
- All adverse events occurring 0-30 days after each dose;
- Adverse events of special interest occurring from the first dose to 30 days after full immunization;
- Serious adverse events occurring from the first dose to 6 months after full immunization.

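### The suspected-zoster definition has no injection-site exclusion, so read literally, ordinary pain or rash after a deltoid injection counts towards the only AESI endpoint

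*Protocol*

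**What the plan says.** The Definitions of Terms, under HZ Suspected Cases, read: "Suspected herpes zoster (HZ) cases meet at least one of the following criteria: a) Unilateral pain or rash". The other two criteria are grouped vesicles in a one-sided dermatomal pattern, and neuralgia. The first criterion has no condition on dermatome, site, duration or alternative cause.

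Section 7.4.7 makes suspected zoster the sole AESI: "AESIs, specifically suspected cases of herpes zoster, will be collected from the first dose through 30 days after completing the full immunization". Section 2.2.2 lists as a secondary safety endpoint "Incidence of adverse events of special interest (AESIs) from the first dose through 30 days after full immunization". Section 8.4.4 analyses it by group, System Organ Class and Preferred Term, with events, subjects and incidence, and does not restrict it to confirmed cases: "Adverse events of special interest occurring from the first dose to 30 days after full immunization".

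Under Section 5.3 the vaccine is "injected intramuscularly into the deltoid muscle". Section 3.1.3.2 lists the solicited local reactions as "Pain, pruritus, induration, swelling, rash, redness".

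Section 3.1.1.2 asks for qPCR on skin-lesion samples from suspected cases where these can be obtained. A Clinical Event Committee appears in the abbreviation list, but no section describes adjudication of suspected cases.

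Among the second-dose exclusions in Section 6.1.2 (also in the Synopsis and Section 4.4) is "Suspected varicella-zoster virus (VZV) infection after the first dose of vaccination", a term the protocol does not define.

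**The concern.** A deltoid injection gives one-sided local pain, and sometimes a one-sided rash. Pain and rash are the two words of the first criterion, and both are solicited local reactions. Nothing says that a reaction recorded in that category is not also a suspected zoster case. A subject with a sore arm on Day 1 therefore meets the definition of the only AESI.

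What is at stake is the pooled AESI incidence by arm. Applied literally, the definition makes that figure largely a second count of local reactogenicity, and the arms differ in reactogenicity for reasons unrelated to zoster. A lower suspected-zoster rate with LZ901 could simply mean fewer sore arms. If investigators instead discount arm pain, each does so by a personal rule, and from the second dose they know which vaccine was given.

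**Working it through.** The protocol gives no expected AESI count, so there is no figure of its own to reproduce. The pain rate can be checked: 26/149 = 17.45%, and the other Phase II percentages for the 100 µg group fit the same denominator (40/149 = 26.85%, 9/149 = 6.04%, 3/149 = 2.01%).

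**Inputs**

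| Input | Value | Source |
|---|---|---|
| Subjects per arm | 150 | Section 3.1, Table 3 |
| Injection-site pain, LZ901 100 µg | 17.45% | Section 1.2.2 (Phase II) |
| Background zoster incidence | 5 per 1000 per year (age 50–59) to 10 per 1000 per year (60 and over) | Section 1.1 |
| AESI window | about 60 days (LZ901: 30 + 30); about 90 days (control: 60 + 30) | Sections 3.1 and 7.4.7; visit windows ignored |
| Control injection-site pain | not given; assumed 17.45% to 80% | assumption |

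**1. Literal cases in the LZ901 arm from injection-site pain alone**

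150 × 0.1745 = 26.2, about 26 subjects.

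**2. True zoster expected, with no vaccine effect** (subjects × annual incidence × days/365)

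- LZ901, 60 days: 150 × 0.005 × 60/365 = 0.12, to 150 × 0.010 × 60/365 = 0.25.
- Control, 90 days: 150 × 0.005 × 90/365 = 0.18, to 150 × 0.010 × 90/365 = 0.37.
- Whole trial: 0.31 to 0.62.

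**3. Ratio in the LZ901 arm**

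26.2/0.247 = 106, to 26.2/0.123 = 212.

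**4. Share of all literal AESI cases that are injection-site pain**

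- Control pain 17.45%, higher incidence: (26.2 + 26.2)/(52.4 + 0.62) = 98.8%.
- Control pain 80%, lower incidence: (26.2 + 120)/(146.2 + 0.31) = 99.8%.

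**5. Difference between arms**

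Over the assumed control range, literal cases from pain number 26 to 120 of 150 in the control arm against 26 of 150 in the LZ901 arm. The gap runs from 0 to 80 − 17.45 = 62.55 percentage points. The protocol does not fix where in that range it lies, but it points away from zero. Section 3.2.3.1 reports any adverse event in 100% of active-control subjects in Phase I against 30% at the high dose, and Section 1.1 says that local pain with the control vaccine's type of adjuvant can persist for two to three weeks. The 100% covers all adverse events and is not a pain rate.

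**The case against.** The strongest reply is that nobody would apply the definition mechanically. It defines a suspected zoster case. Injection-site reactions have their own category, grading table and analysis, and the sampling instructions in Sections 3.1.1.2 and 5.1.5 presume lesions. That reply stands in part: 26 subjects is what the text yields when followed literally, not a forecast of what sites will record. But the protocol states no rule for discounting arm pain, so the alternative to the literal count is unstated judgement, open-label from the second dose.

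A broad definition is also reasonable for case finding, where it only triggers a closer look. Here the suspected case is itself the event counted.

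Four stronger readings might be inferred, and the documents do not support them:

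- *That the trial loses the ability to show a zoster signal.* Section 8.4.4 tabulates AESIs by Preferred Term. Injection-site pain and zoster would normally code to different terms, so zoster stays visible in its own row. With fewer than one true case expected in the whole trial, no definition could show a signal.
- *That the endpoint is certain to be swamped.* This depends on literal application.
- *That qPCR results are ignored.* The protocol orders the test and does not say how the result enters the tables. Silence is not a rule to disregard it.
- *That arm pain after the first dose bars the second.* The second-dose criterion refers to suspected VZV infection, not to the defined term for suspected zoster. The link is possible but not stated.

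**Conclusion.** The point holds as a defect in how one listed secondary safety endpoint is defined. Read as written, about 26 of 150 LZ901 subjects would count as AESI cases from injection-site pain alone, against 0.12 to 0.25 true zoster cases expected in that arm. This rests on the Phase II pain rate carrying over, background incidence with no vaccine effect, a 60-day window and literal use of the first criterion. Under the assumed control pain rates, 98.8% to 99.8% of literal AESI cases across the trial would be injection-site pain. The size of the difference between arms cannot be fixed from the documents, only its likely direction, towards more cases with the control vaccine.

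The damage is confined to the pooled AESI incidence and its comparison between arms. The hypotheses in Section 8.1, the sample size in Section 8.2 and the rows by System Organ Class and Preferred Term do not depend on this definition.

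**What to change.** 1. For counting the AESI endpoint only, add a sentence to the definition, or to Section 7.4.7: a reaction at the injection site that is recorded as a local adverse event does not by itself make a suspected HZ case. There is no need to make the first criterion dermatomal, which would narrow a screening definition at every body site.
2. Report qPCR-confirmed cases beside suspected cases. Pain without a lesion cannot be swabbed, so both rows are needed. The table layout may sit in the SAP.
3. Reconcile the suspected-VZV-infection criterion for the second dose (Synopsis, Sections 4.4 and 6.1.2) with the defined term for suspected zoster, so that it is clear whether they are the same thing. What the clinical rule should be is for the sponsor and investigators; this review proposes none.

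The cost is wording: no new visits, samples or tests, since the qPCR is already planned. The small downside is that zoster confined to the injection site would be counted only through the vesicle criterion or a positive qPCR.
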